8.3.4.2. LEAP Siblings and Parents

The peanut specific IgE measurements (kU/L) for the LEAP Siblings in the ITT population will be compared between LEAP Consumers and LEAP Avoiders. The measurements will be log-transformed for analysis. The log-transformed data will be analyzed using a linear mixed effects model with a random family effect included to account for the clustering of siblings within family units and the analysis of multiple siblings. Older Siblings and Younger Siblings will be analyzed separately.

The same statistical methodology will be repeated on the immunoglobulin measurements for all tested allergens.

The same statistical methodology will also be repeated for the LEAP Parents in the ITT population on all tested allergens.

8.3.5. Secondary Endpoint 4: Eczema severity

Scoring Atopic Dermatitis (SCORAD) assessment will be used to assess severity of eczema symptoms at V144 in LEAP Participants and Siblings.

Eczema severity will also be analyzed using severity categories derived from the SCORAD as follows:

- No eczema: SCORAD = 0
- Mild eczema: SCORAD >0 to <15
- Moderate eczema: SCORAD \geq 15 to < 40
- Severe eczema: SCORAD \geq 40

8.3.5.1. LEAP Participants

The SCORAD score for the LEAP Participants in the ITT population will be compared between LEAP Consumers and LEAP Avoiders using the most appropriate parametric or non-parametric tests (e.g. Wilcoxon and t-test) for the SCORAD data. The data will first be tested to determine normality. If the data are not normal then a Wilcoxon test will be run. If the data are normal then tests will be run to determine if the variances are equal between the two groups. If the variances

are equal, a two sample t-test assuming equal variances will be used; otherwise, a two sample t-test assuming unequal variances will be used.

Eczema severity categories for the LEAP Participants in the ITT population will be compared between LEAP Consumers and LEAP Avoiders using a Fisher's exact test.

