# 9.3 SAMPLE SIZE

# **LEAP Participants**

The sample size is based on the number of children likely to be available to enroll in the study. As shown in the Figure 1 LEAP Screening, Participant and Sibling Cohorts, there are 311 LEAP avoiders and 319 LEAP consumers (total 630) potentially eligible for enrollment. In the LEAP study, the rate of peanut allergy was 3.2% among consumers and 17.2% among avoiders at 60 months of age. We assume that the rates will not change markedly between month 60 and 144. We wish to detect a difference between the groups that are similar to that detected at 60 months. 88.5% of those potentially eligible enrolled in the follow on LEAP-On Study. We assume a lower percentage of those potentially eligible will enroll in this study.

For example, if 80% of those potentially eligible enroll, the true rate of allergy among LEAP consumers at 144 months is 6%, and the true rate of allergy among LEAP avoiders at 144 months is 15%, there is 91% power to detect a difference with a two-sided type I error of 0.05 between the groups. If only 70% enroll and other assumptions remain constant, there would be about 87% power to detect a difference.

Other examples are shown in Figure 3.

Three possible recruitment rates are shown in the left, middle and right panels. In each panel, the power to detect a difference, with a two-sided type I error of 0.05, between groups is shown on the vertical axis for different assumptions regarding the true underlying allergy rates in the consumer and avoider groups at month 144. In each panel contour lines display rates in consumers of 2%, 4%, 6%, 8% and 10% while the horizontal axis displays a range of rates in avoiders of 10 to 25%

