8.3.5.2. LEAP Siblings

The SCORAD score for the LEAP Siblings in the ITT population will be compared between LEAP Consumers and LEAP Avoiders using a linear mixed effects model with a random family effect included to account for the clustering of siblings within family units and the analysis of multiple siblings. Older Siblings and Younger Siblings will be analyzed separately.

Eczema severity categories for the LEAP Siblings in the ITT population will be compared between LEAP Consumers and LEAP Avoiders using an ordinal logistic regression mixed effects model with a random family effect included to account for the clustering of siblings within family units and the analysis of multiple siblings. Older and Younger Siblings will be analyzed separately.

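### Ordered eczema severity bands in LEAP participants are compared with an order-blind Fisher's exact test that gives no effect estimate, while siblings get an ordinal model

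*SAP*

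**What the plan says.** Secondary endpoint 4 is eczema severity by SCORAD. SAP 8.3.5 introduces the bands as an addition to the score: "Eczema severity will also be analyzed using severity categories derived from the SCORAD as follows". The bands are none (0), mild ("Mild eczema: SCORAD >0 to <15"), moderate (15 to below 40) and severe (40 or more).

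For LEAP participants, SAP 8.3.5.1 plans two comparisons between arms:

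- The SCORAD score goes through a normality test. "If the data are not normal then a Wilcoxon test will be run"; otherwise a t-test is used.
- For the bands: "Eczema severity categories for the LEAP Participants in the ITT population will be compared between LEAP Consumers and LEAP Avoiders using a Fisher's exact test". No significance level or effect measure is named for this test.

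For siblings, SAP 8.3.5.2 compares the same bands "using an ordinal logistic regression mixed effects model with a random family effect", with older and younger siblings analysed separately.

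The table of secondary analyses in Protocol 9.2 covers only the SCORAD score for this endpoint, so the band comparison is an SAP addition. SAP section 11, on changes from the protocol, does not mention it.

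**The concern.** The bands are ordered by construction. On a 2×4 table Fisher's exact test treats them as four unrelated labels, so swapping mild and severe would leave the p-value unchanged. It spreads its sensitivity over three degrees of freedom, whereas a shift towards milder or more severe eczema needs only one. It also produces a p-value and nothing else.

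The sibling analysis shows that the SAP already regards this variable as ordinal. Clustering within families explains the random effect there. It does not explain why the ordering is dropped for participants, who are the randomised cohort. As planned, siblings get a common odds ratio and participants get none.

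At stake are power and interpretability in one supplementary analysis of a secondary endpoint. The sample cannot be enlarged to compensate, because it is capped by the original LEAP cohort.

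**Working it through.** **1. Arm sizes.** Protocol 9.3 states that "there are 311 LEAP avoiders and 319 LEAP consumers (total 630) potentially eligible for enrollment". At its 80% enrolment example, 0.8 × 311 = 249 and 0.8 × 319 = 255. These sizes can be checked against the only participant power figure given, for peanut allergy at 15% against 6%, two-sided 0.05:

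- Pooled rate = (249 × 0.15 + 255 × 0.06)/504 = 0.1045.
- Null SE = √[0.1045 × 0.8955 × (1/249 + 1/255)] = 0.02725.
- Alternative SE = √(0.15 × 0.85/249 + 0.06 × 0.94/255) = 0.02708.
- Power = Φ[(0.09 − 1.96 × 0.02725)/0.02708] = Φ(1.351) = 91.2%, against 91% stated. With 218/223 (70% enrolment) it is 87.2%, against 87% stated.

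The arm sizes are therefore right. The documents give no power, effect size or band distribution for eczema severity, so everything below rests on assumed values and an assumed two-sided 0.05 level.

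**2. Large-sample comparison.** Under proportional odds the ordinal test is close to a 1-df chi-square test with noncentrality λ. At best, the unordered test puts the same λ on 3 df. The critical values are 3.841 and 7.815.

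| λ | Ordinal power (1 df) | Unordered power (3 df) | Loss (points) |
|---|---|---|---|
| 2.06 | 30% | 19.7% | 10.3 |
| 3.84 | 50% | 34.5% | 15.5 |
| 4.90 | 60% | 43.2% | 16.8 |
| 6.17 | 70% | 53.1% | 16.9 |
| 7.85 | 80% | 64.5% | 15.5 |
| 10.51 | 90% | 78.4% | 11.6 |
| 13.00 | 95% | 87.1% | 7.9 |

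The loss peaks at about 17 points. For 80% power the unordered test needs λ = 10.90 instead of 7.85, that is 10.90/7.85 = 1.39, or about 39% more participants.

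**3. One case by hand.** Assume shares of 50/30/17/3% (none/mild/moderate/severe) in one arm and a common odds ratio of 1.6.

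- Cumulative odds of 1, 4 and 32.3 become 1.6, 6.4 and 51.7, so the other arm has about 61.5/24.9/11.6/1.9%.
- Mean shares p̄ are 0.558, 0.274, 0.143 and 0.024, and 1 − Σp̄³ = 0.802.
- Information V = [249 × 255 × 504/(3 × 505²)] × 0.802 = 41.83 × 0.802 = 33.6.
- λ = (ln 1.6)² × V = 0.2209 × 33.6 = 7.4.
- Power is about 78% on 1 df and 62% on 3 df.

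**4. Simulation with the exact test.** This compares the exact 2×4 Fisher (Freeman–Halton) test with the tie-corrected Wilcoxon test on the bands, which is the score test of the proportional-odds model. There were 249/255 per arm and 2,500 replicates.

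| Assumed shares | OR | Fisher | Ordinal | Loss (points) |
|---|---|---|---|---|
| 50/30/17/3 | 1.6 | 61% | 77% | 16.8 |
| 60/25/13/2 | 1.6 | 57% | 73% | 16.7 |
| 60/25/13/2 | 1.7 | 69% | 82% | 13.1 |
| 75/17/7/1 | 1.8 | 62% | 74% | 12.2 |
| 30/35/28/7 | 1.5 | 53% | 69% | 16.5 |

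A wider grid used five share patterns and odds ratios of 1.3 to 1.8. It was run with 249/255 and with 187/191 per arm (60% of those eligible), since SCORAD is not done at telephone visits (Protocol 6.2.3). The loss ran from about 6 to 17 points. Where ordinal power was 50 to 80%, the loss was about 12 to 17, and losses near 12 came only with a severe band of 1 to 2%. Rejection under no difference was close to 5% for both tests.

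**5. Differences that are not a uniform shift.** The ranking reverses. If only the mild/moderate split differs, Fisher has 71% power and the ordinal test 9%. If the difference is concentrated in the severe band (60/20/13/7 against 62/21/15/2), it is 64% against 13%.

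**6. The planned test on the score.** In four matched scenarios (latent logistic severity, zero below a threshold), Wilcoxon on the SCORAD score has 79, 73, 75 and 74% power. The ordinal test on the bands has 77, 73, 74 and 69%.

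**The case against.** The strongest reply is that the endpoint already has an order-using test. SAP 8.3.5.1 first compares the SCORAD score itself, on a finer scale than four bands, and step 6 shows that this test has at least about the power of an ordinal test on the bands. A reader might infer that eczema severity as an endpoint gives up 15 points or more, or that a shift between the arms is likely to go unnoticed. The documents do not support that, because the loss falls on the band analysis alone.

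A reader might also infer that the power is lost for no return. That does not stand either. Fisher's test needs no proportional-odds assumption, stays valid with a sparse severe band, and detects the patterns in step 5 that an ordinal test nearly misses.

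Two further points carry some weight. SAP section 4 reports categorical variables as counts and percentages, so the direction could be read off the table. Participant and sibling methods also differ throughout the SAP because of clustering, and no comparison of the two cohorts on eczema severity is planned.

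What remains is that the score test supplies no odds ratio across the severity bands, reading direction from a table is informal, and clustering gives no reason to drop the ordering in participants.

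**Conclusion.** The point holds as a cheap improvement to a supplementary analysis. Fisher's exact test is valid here, but it ignores the order of the bands and leaves the randomised cohort without the effect estimate that siblings receive.

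Under proportional odds with about 250 per arm, the cost is about 15 to 17 points of power by the large-sample calculation when the ordinal test has 50 to 80% power. It is somewhat less if the severe band is very sparse, about 10 points at 30% ordinal power and about 12 at 90%. These figures depend on assumed band shares, odds ratios and a two-sided 0.05 level. They do not apply, and the advantage can reverse, if the arms differ other than by a uniform shift. The case for a direction and an estimate does not depend on any of these assumptions.

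**What to change.** In SAP 8.3.5.1, make the band comparison a proportional-odds logistic model with arm as the only term, reporting the common odds ratio with its 95% CI, in line with 8.3.5.2. Keep the 2×4 table of counts and percentages, with Fisher's exact test as a supportive check. A Wilcoxon test on the bands would serve for the hypothesis test but would not supply the odds ratio.

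The cost is one sentence in the SAP. Protocol 9.2 needs no change, since it does not plan the band analysis. The small downside is reliance on the proportional-odds assumption, and the retained Fisher's test is the check on departures from it.

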8.3.5.2. LEAP Siblings

The SCORAD score for the LEAP Siblings in the ITT population will be compared between LEAP Consumers and LEAP Avoiders using a linear mixed effects model with a random family effect included to account for the clustering of siblings within family units and the analysis of multiple siblings. Older Siblings and Younger Siblings will be analyzed separately.

Eczema severity categories for the LEAP Siblings in the ITT population will be compared between LEAP Consumers and LEAP Avoiders using an ordinal logistic regression mixed effects model with a random family effect included to account for the clustering of siblings within family units and the analysis of multiple siblings. Older and Younger Siblings will be analyzed separately.

8.3.6. Secondary Endpoint 5/6: Eczema prevalence

The eczema evaluation assessments and medical history will be used to determine the prevalence of eczema at V144 in all 4 cohorts (LEAP Participants, Older Siblings, Younger Siblings, and Parents). As noted in section 8.3.5, SCORAD assessments were only performed on LEAP Participants and Siblings at V144. Participants who report a history of eczema that has not resolved will be classified as having eczema.

8.3.6.1. LEAP Participants

The prevalence of eczema in the LEAP Participants in the ITT population will be compared between LEAP Consumers and LEAP Avoiders using a two-tailed, chi-squared test at the 0.05 level of significance.

8.3.6.2. LEAP Siblings and Parents

The prevalence of eczema in the LEAP Siblings in the ITT population will be compared between LEAP Consumers and LEAP Avoiders using a logistic regression model with a random family effect included to account for the clustering of siblings within family units and the analysis of multiple siblings. Older Siblings and Younger Siblings will be analyzed separately.

The same statistical methodology will be repeated for the LEAP Parents in the ITT population.

8.3.7. Secondary Endpoint 5/6: Asthma prevalence

The asthma evaluation assessments, allergen test results, medical history and concomitant medications data will be used in all 4 cohorts (LEAP Participants, Older Siblings, Younger Siblings, and Parents) to determine which participants meet the protocol definition of asthma diagnosis provided in protocol section 3.3.4:

Asthma will be diagnosed if one of the following three definitions is met:

- A history of cough, wheeze, or shortness of breath that meets all three of the following criteria: (1) was responsive to therapy with bronchodilators on two or more occasions in the previous 24 months, and (2) required one visit to a physician in the previous 24 months, and (3) occurred during the night, during early morning, or upon exercising in the intervals between exacerbations at any time in the previous 12 months, or
- Participant report of an asthma diagnosis on the Medical History Case Report Form (CRF) with current use of asthma medications (Short-acting beta-agonist [SABA] or controller) on the Concomitant Medications CRF, or
- Participant report of transient wheeze on exposure to a suspected allergen with confirmatory allergy tests.

8.3.7.1. LEAP Participants

The prevalence of asthma in the LEAP Participants in the ITT population will be compared between LEAP Consumers and LEAP Avoiders using a two-tailed, chi-squared test at the 0.05 level of significance.

8.3.7.2. LEAP Siblings and Parents

The prevalence of asthma in the LEAP Siblings in the ITT population will be compared between LEAP Consumers and LEAP Avoiders using a logistic regression model with a random family effect included to account for the clustering of siblings within family units and the analysis of multiple siblings. Older Siblings and Younger Siblings will be analyzed separately.

The same statistical methodology will be repeated for the LEAP Parents in the ITT population.

8.3.8. Secondary Endpoint 5/6: Rhinitis prevalence

The rhinitis evaluation assessments, allergen test results and medical history data will be used in all 4 cohorts (LEAP Participants, Older Siblings, Younger Siblings and Parents) to determine which participants meet the protocol definition of rhinitis diagnosis provided in protocol section 3.3.3:

Perennial rhinitis/rhinoconjunctivitis: Sensitization to a perennial allergen and clinical history of rhinoconjunctivitis symptoms with evidence of sensitization and corresponding clinical history to the relevant allergen.

Seasonal rhinitis/rhinoconjunctivitis. Sensitization to a seasonal allergen and clinical history of rhinoconjunctivitis symptoms with evidence of sensitization and corresponding clinical history to the relevant allergen.

Sensitization to relevant allergens will be defined as:

- a) Allergen specific IgE \geq 0.35 kU/L, or
- b) Skin prick test to allergen \geq 3 mm.

8.3.8.1. LEAP Participants

The prevalence of rhinitis in the LEAP Participants in the ITT population will be compared between LEAP Consumers and LEAP Avoiders using a two-tailed, chi-squared test at the 0.05 level of significance.

8.3.8.2. LEAP Siblings and Parents

The prevalence of rhinitis in the LEAP Siblings in the ITT population will be compared between LEAP Consumers and LEAP Avoiders using a logistic regression model with a random family effect included to account for the clustering of siblings within family units and the analysis of multiple siblings. Older Siblings and Younger Siblings will be analyzed separately.

The same statistical methodology will be repeated for the LEAP Parents in the ITT population.

8.3.9. Secondary Endpoint 7: Peanut allergy

Peanut allergy status in the LEAP Siblings and LEAP Parents at V144 will be determined using the same criteria for the determination of peanut allergy status in LEAP Participants, as described in section 8.2.1.1.

The proportion of LEAP Siblings in the ITT population with peanut allergy will be compared between the LEAP Consumers and LEAP Avoiders using a logistic regression model with a random family effect included to account for the clustering of siblings within family units and the analysis of multiple siblings. Older Siblings and Younger Siblings will be analyzed separately.

The same statistical methodology will be repeated for the LEAP Parents in the ITT population.

8.3.9.1. Assessment of Prediction Model

The performance of the prediction model used in the definition of peanut allergy in LEAP Trio will be assessed.

The outcomes of the prediction model (allergic or tolerant) will be compared to the outcomes of the peanut oral food challenges conducted in LEAP Trio, and several model fit diagnostic metrics will be used to assess the prediction model's performance.

The outcomes of the prediction model (allergic or tolerant) will also be compared to the tolerant peanut allergy status that was determined by the participants' responses to the peanut consumption questions.

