## 3.3 STUDY DEFINITIONS

#### 3.3.1 Determination of Primary Peanut Allergy

Peanut allergy status will be determined by peanut challenge where possible. Peanut challenges are described in section 6.7. Participants meeting criteria for peanut oral allergy syndrome in the absence of primary peanut allergy as described in section 3.3.5 will not be considered peanut allergic.

Individuals consuming at least 2g of peanut protein without reaction on at least one occasion in the last year will be considered peanut tolerant.

If oral challenge is not possible and participants do not meet the above criteria for tolerance, peanut allergy status will be determined by an internally and externally validated novel peanut allergy prediction model, the manuscript for which is currently in preparation: *Developing a Prediction Model for Determination of Peanut Allergy Status in The LEAP Trio Study*; Sever ML, Calatroni A, Du Toit G, et al. The model was developed using data from the LEAP participants, and incorporates peanut wheal size (mm), peanut specific IgE (kU/L), IgG4:IgE Ratio and Ara h2 (kU/L). The model performs with high level of accuracy, and continues to perform reasonably well in the context of missing blood or skin prick data. This model replaces the previously specified algorithm for determination of peanut allergy status. The details of the prior algorithm are included in the Appendix 2 for historical reference.

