8.2.1.1. Computation of the Primary Endpoint

Peanut allergy status at V144 will be determined by peanut challenge where possible. Peanut challenges are described in protocol section 6.7. Participants meeting criteria for peanut oral allergy syndrome in the absence of primary peanut allergy as described in protocol section 3.3.5 will not be considered peanut allergic.

Individuals who report consuming at least 2 g of peanut protein without reaction on at least one occasion in the last year will be considered peanut tolerant.

If oral challenge is not possible and participants do not meet the above criteria for tolerance, peanut allergy status will be determined by an internally and externally validated novel peanut allergy prediction model, the manuscript for which is currently in preparation: Developing a Prediction Model for Determination of Peanut Allergy Status in The LEAP Trio Study; Sever ML, Calatroni A, Roberts G, et al. The model was developed using data from the LEAP participants, and incorporates peanut wheal size (mm), peanut specific IgE (kU/L), Ara h1 (kU/L), Ara h2 (kU/L) and Ara h3 (kU/L). The model performs with high level of accuracy, and continues to perform reasonably well in the context of missing blood or skin prick data. This model replaces the previously specified algorithm for determination of peanut allergy status. The V144 assessments with non-missing data will be used as independent variables in the peanut allergy prediction model to impute peanut allergy status. LEAP Participants who do not have an oral food challenge, do not meet the peanut consumption criteria for tolerance and do not have any of the assessments for the peanut allergy prediction model will not be included in the primary analyses of the primary endpoint.

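### The planned check of the prediction model is made in people whose status the model does not set, and its label enters the participant co-primary and secondary endpoint 7 as if observed

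*SAP*

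**What the plan says.** SAP 8.2.1.1 sets peanut allergy status in three steps: challenge where possible; tolerance by a reported intake of at least 2 g of peanut protein without reaction in the last year; otherwise the model. It calls this "an internally and externally validated novel peanut allergy prediction model" and says "The model was developed using data from the LEAP participants". The model runs on whichever Visit 144 predictors are present, and the SAP says that it "continues to perform reasonably well in the context of missing blood or skin prick data". Neither document gives a sensitivity, a specificity or a cut-off.

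SAP 8.3.9 applies the same steps to siblings and parents for secondary endpoint 7. Protocol 6.7.1 and Appendix 1 limit challenges to LEAP participants and siblings under 18.

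SAP 8.3.9.1 plans two comparisons of the model's output. The first is with challenge: "The outcomes of the prediction model (allergic or tolerant) will be compared to the outcomes of the peanut oral food challenges conducted in LEAP Trio". In the second, the output "will also be compared to the tolerant peanut allergy status that was determined by the participants' responses to the peanut consumption questions". Several fit metrics are promised, with no split by cohort or by which predictors were available.

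The predictor lists differ. Beyond wheal size and peanut-specific IgE, Protocol 3.3.1 has "IgG4:IgE Ratio and Ara h2 (kU/L)" and SAP 8.2.1.1 has "Ara h1 (kU/L), Ara h2 (kU/L) and Ara h3 (kU/L)". SAP section 11, on changes from the protocol, does not mention this.

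**The concern.** A classifier should be checked in people like those it will classify. Here the two groups are separated by rule: anyone with a challenge result is not classified by the model. If the model does worse in unchallenged people, the planned metrics will not show it, yet they are the only in-trial evidence for the labels it assigns.

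What is at stake is the participant co-primary and secondary endpoint 7. Both take the label as a known value, so their confidence intervals carry no allowance for classification error. If error is equal in the arms, the odds ratio moves toward 1. If it differs by arm, the odds ratio can move either way. Protocol 1.2 reports that Ara h2-specific IgE, IgG4 and the IgG4:IgE ratio differed between arms at 60 and 72 months, so equal error cannot be taken for granted.

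**Working it through.** **1. Who is checked and who is classified**

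| | Reference in 8.3.9.1 | Status set by model? |
|---|---|---|
| Challenged LEAP participants and siblings under 18 | Allergic or tolerant | No |
| Unchallenged, 2 g rule met | Tolerant only | No |
| Unchallenged, 2 g rule not met | None | Yes |

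The second row has no allergic reference cases, so it informs specificity only, and it takes the intake report as true. No analysis compares that report with challenge in people who have both.

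The groups also differ by design. Protocol 6.2.2 allows no home challenge for anyone at risk of a reaction. Protocol 6.2.3 lets telephone participants supply outside skin-test and IgE results or home-collected blood, so some predictors may be missing. Parents and siblings aged 18 or over can reach a status only by the 2 g report, which yields tolerant, or by the model. Every allergic label among them therefore comes from the model.

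**2. Whether the label is ever varied**

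The participant co-primary is an unadjusted logistic regression on the single status (SAP 8.2.1.2). Sensitivity analyses 8.2.1.2.1 to 8.2.1.2.6 impute only missing determinations, and a model-set status counts as determined. Three of them (8.2.1.2.2, .4 and .6) take their transition rates from Visit 144 statuses that include model-set ones. None excludes or varies the label.

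**3. The plan's own power figure**

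Inputs from Protocol 9.3: 311 avoiders and 319 consumers, 80% enrolment (249 and 255), 15% against 6%, two-sided 0.05.

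Power = Φ[(|p1 − p2| − 1.96·SE0)/SE1], with SE0 from the pooled rate and SE1 from the separate rates.

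- Pooled rate = (249×0.15 + 255×0.06)/504 = 0.1045; SE0 = 0.02725; SE1 = 0.02708.
- Power = Φ[(0.09 − 0.0534)/0.02708] = Φ(1.35) = 91.2%, against 91% stated.
- At 70% enrolment (218 and 223): 87.2%, against about 87% stated.

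**4. Illustration of unpropagated error**

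The documents give neither the model-set share f nor the model's accuracy. Assumed: f from 10% to 40%, sensitivity (Se) and specificity (Sp) from 0.80 to 0.95, equal in both arms.

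Observed rate = (1 − f)p + f[p·Se + (1 − p)(1 − Sp)]

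Example, f = 0.40, Se = Sp = 0.80:
- Avoiders: 0.6×0.15 + 0.4×(0.12 + 0.17) = 0.206
- Consumers: 0.6×0.06 + 0.4×(0.048 + 0.188) = 0.1304

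| f | Se = Sp | Avoiders | Consumers | Odds ratio | Power |
|---|---|---|---|---|---|
| 0 | – | 15.0% | 6.0% | 0.36 | 91.2% |
| 10% | 0.95 | 15.35% | 6.44% | 0.38 | 89.7% |
| 20% | 0.90 | 16.4% | 7.76% | 0.43 | 84.8% |
| 40% | 0.90 | 17.8% | 9.52% | 0.49 | 77.4% |
| 40% | 0.80 | 20.6% | 13.04% | 0.58 | 62.2% |

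**5. Whether the direction of non-transfer is fixed**

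Assume specificity 0.999 in non-sensitized people, specificity 0.70 in sensitized-tolerant people, and sensitivity 0.85. Counts are non-sensitized / sensitized-tolerant / allergic.

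- Challenged, 340/30/30: (339.66 + 21 + 25.5)/400 = 96.5%
- Model-classified, 10/20/20: (9.99 + 14 + 17)/50 = 82.0%
- Model-classified, 40/5/5: (39.96 + 3.5 + 4.25)/50 = 95.4%
- Model-classified, 45/3/2: (44.955 + 2.1 + 1.7)/50 = 97.5%

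The gap is large in the second case and reversed in the last. All four mixes are assumed.

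**The case against.** The strongest reply is that the model is stated to be validated internally and externally, so 8.3.9.1 is an extra check and reduced-data performance may already have been shown. That may be so, but the results sit in a manuscript in preparation, neither document gives a figure, and the two predictor lists leave open which model was validated.

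A reader might infer three stronger claims that the documents do not support.

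- **That the check will overstate accuracy.** Step 5 shows that this depends on case mix. People not challenged because their allergy is plain could be easier to classify. Home visits keep skin and blood testing, so unchallenged people may have full predictors; no frequency of partial data is given.
- **That it largely re-tests the development children.** Protocol 9.3 puts younger siblings at 222 + 207 + 80 = 509, against 630 LEAP children. LEAP children are then 630/1,139 = 55% of that pool, or 630/1,376 = 46% if all 746 surveyed siblings counted. The number actually challenged is unknown, and Visit 144 data are new measurements at a later age. What stands is that LEAP children are included and not separated.
- **That no result is free of the model's error.** The sibling co-primary rests on IgE and skin test (SAP 8.2.2.1), and the within-consumer McNemar test admits only participants with a determinate Visit 144 challenge (SAP 8.2.1.3).

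It is also fair that the SAP describes the model's output only as allergic or tolerant, so usable predicted probabilities cannot be assumed.

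**Conclusion.** The point holds with limited scope. The in-trial check has a reference able to show both kinds of error only in people the model does not classify, and it pools the development cohort with siblings. Its result may not transfer to model-classified people and may overstate accuracy there. Direction and size cannot be settled from the documents.

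For the participant co-primary and secondary endpoint 7, the label is treated as observed and no planned analysis tests reliance on it. The illustrated loss for participants runs from 1.5 power points (91.2% to 89.7%) to 29 points (91.2% to 62.2%). This rests on an assumed share, assumed accuracy and equal error by arm; it is a range, not an estimate. If few statuses are model-set, the effect is small, which is why that count should be reported first.

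**What to change.** - **Counts.** Report the number and share of statuses set by challenge, by the 2 g report and by the model, by arm and cohort.
- **Performance.** In SAP 8.3.9.1, give sensitivity and specificity with intervals separately for LEAP participants and siblings, among challenged people not meeting the 2 g rule, and with predictors blanked to the missing patterns seen in model-classified people.
- **Intake report.** Cross-tabulate the 2 g report against challenge outcome in people with both.
- **Sensitivity analyses.** Re-run the participant co-primary and endpoint 7 without model-set statuses and, where predicted probabilities are available, with status multiply imputed from them. Exclusion alone may select on allergy, so read the two together. For parents and siblings aged 18 or over, exclusion leaves no allergic cases, so only imputation is informative.
- **Predictors.** Reconcile Protocol 3.3.1 with SAP 8.2.1.1, state which model was validated, and record the change in SAP section 11.

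This uses data already planned and adds no procedures. The cost is more analysis work and slightly less favourable precision. Imputation also depends on the model's probabilities being available and reasonably calibrated.
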